5.3.1.2. Other Patient Reported Outcome

Measurement	Formula
Daily activities resumption	
Daily activities resumption will be assessed once daily by means of the question 'Over the past 24 hours, how much has influenza interfered with your ability to carry out your daily activities?'
 
The responses will be dichotomized: 'Not at all' and 'A little bit' will be considered as category “returned to daily activities” and responses 'Somewhat', 'Quite a Bit' and 'Very much' will be considered in category “not returned to daily activities”.

Time to return to daily activities (hours) [Time-to event]	The time to return to daily activities is defined as the time in hours from initiation of study treatment to the first of a successive series of 2 recordings in which the response is considered as returned to daily

	
activities. The 2 successive recordings may have been done over 3 scheduled successive analysis timepoints, in case of 1 missing in between timepoint.
 
In case the return to daily activities is not achieved, data will be censored.
 
Censoring will be done as follows:
 
 1) Last non-missing record indicates return to daily activities (but insufficient recordings) 
Censoring will be done at the last non-missing record
 2) Last non-missing record does not indicate return to daily activities 
Censoring will be done one day (24 hours) after the last non-missing record.
 
The time to return to daily activities is calculated as: (Date and time of event (actual) or censoring - date and time of first dose of study drug)/3600, rounded to one decimal.
																														

Patient Global Impression of Severity of Influenza symptoms
	
The PGIS captures daily influenza symptom severity from the subjects’ perspective per timepoint. Responses will be categorized as: “No Flu symptoms today”, “Mild”, "Moderate", "Severe" or “Very Severe”.
																														

Patient global Impression of Change in Influenza symptoms
	
The PGIC^[3] is aimed to capture the subject’s perceptions of improvement or deterioration in the severity of influenza symptoms compared to when the subject arrived to the investigational site for influenza treatment and is done per timepoint.
 
Categories are: “Much better”, “Somewhat better”, “A little better” “About the same”, “A little worse”, “Somewhat worse” and “Much worse”.
																														

EQ-5D dimension parameters: Mobility, Self-care, Usual activities, Pain/discomfort, Anxiety/depression
	
The EQ-5D^[2] descriptive system consists of 5 dimensions (mobility, self-care, usual activities, pain/discomfort, anxiety/depression) with 5 possible levels (no problems (level code = 1), slight problems (level code = 2), moderate problems (level code = 3), severe problems (level code = 4), extreme problems (level code = 5)).
 
Table 7: EQ-5D Dimensions
 
  
 Dimension	Level	Interpretation	
   
 1	Mobility	1	No problems	I have no problems in walking about	
 
 		2	Slight problems	I have slight problems in walking about	
 
 		3	Moderate problems	I have moderate problems in walking about	
 
 		4	Severe problems	I have severe problems in walking about	
 
 		5	Extreme problems	I am unable to walk about	
  
	Dimension		Level		Interpretation	1	Mobility	1	No problems	I have no problems in walking about			2	Slight problems	I have slight problems in walking about			3	Moderate problems	I have moderate problems in walking about			4	Severe problems	I have severe problems in walking about			5	Extreme problems	I am unable to walk about
Dimension		Level		Interpretation																											
1	Mobility	1	No problems	I have no problems in walking about																											
		2	Slight problems	I have slight problems in walking about																											
		3	Moderate problems	I have moderate problems in walking about																											
		4	Severe problems	I have severe problems in walking about																											
		5	Extreme problems	I am unable to walk about																											

	2	Self-care	1 No problems	I have no problems washing or dressing myself
			2 Slight problems	I have slight problems washing or dressing myself
			3 Moderate problems	I have moderate problems washing or dressing myself
			4 Severe problems	I have severe problems washing or dressing myself
			5 Extreme problems	I am unable to wash or dress myself
	3	Usual activities	1 No problems	I have no problems doing my usual activities
			2 Slight problems	I have slight problems doing my usual activities
			3 Moderate problems	I have moderate problems doing my usual activities
			4 Severe problems	I have severe problems doing my usual activities
			5 Extreme problems	I am unable to do my usual activities
	4	Pain/discomfort	1 No problems	I have no pain or discomfort
			2 Slight problems	I have slight pain or discomfort
			3 Moderate problems	I have moderate pain or discomfort
			4 Severe problems	I have severe pain or discomfort
			5 Extreme problems	I have extreme pain or discomfort
	5	Anxiety/depression	1 No problems	I am not anxious or depressed
			2 Slight problems	I am slightly anxious or depressed
			3 Moderate problems	I am moderately anxious or depressed
			4 Severe problems	I am severely anxious or depressed
			5 Extreme problems	I am extremely anxious or depressed
EQ-5D visual analogue scale (VAS)	EQ-5D VAS is a continuous score ranging from 0 (worst health you can imagine) to 100 (best health you can imagine).			
EQ-5D VAS change from baseline	EQ-5D VAS post-baseline value – EQ-5D VAS baseline value			
EQ-5D VAS clinically relevant change from baseline	The change from baseline in EQ-5D VAS will be categorized in two ways: 1. $\leq -7, -6$ to $6, \geq 7$ 2. $\leq -10, -9$ to $9, \geq 10$			
EQ-5D Valuation index	EQ-5D Valuation index summarizes the information of the 5 dimensions of the descriptive system. a. Assign the level code 1, 2, 3, 4 and 5 to each level of the 5 dimensions (see table) b. Create a health state for each patient-time point combination. A health state is a combination of 5 level codes; one level code for each dimension. The dimensions are ordered as described in the table above. Eg, health state 12543 indicates ‘no problems in walking about, slight problems washing or dressing myself, unable to do my			

	
usual activities, severe pain or discomfort, moderately anxious or depressed’.
 
c. Assign an index value to each health state as defined in Attachment 5 where EQ-5D health state is converted to a single summary index by applying a formula that essentially attaches weights to each of the levels in each dimension. The algorithm is based on the valuation of EQ-5D health states using the UK TTO (=time trade-off method) based value set.

EQ-5D Valuation index change from baseline
	
EQ-5D valuation index post-baseline value – EQ-5D valuation index baseline value

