5.3.2.2. Other Patient Reported Outcome

Time to return to daily activities

Time to return to daily activities will be analyzed by Kaplan-Meier analysis, Gehan-Wilcoxon test, log-rank test, AFT model, and Cox proportional hazards model.

The AFT and Cox models will include the fixed categorical effects for treatment (with placebo as the reference) and stratification factors.

Patient global Impression parameters and daily activities resumption

The subject's perception of severity and change of influenza symptoms (PGIS and PGIC) and the daily activities resumption will be tabulated per parameter and per category by analysis timepoint using frequency tabulations.

EQ-5D dimensions

Tabulations of the number (and percentage) of subjects per parameter, response and timepoint will be shown per treatment group.

EQ-5D VAS, EQ-5D Valuation index

The actual values and changes from baseline will be shown descriptively and by mean (SE) plots per analysis visit.

The proportion of subjects with a clinically relevant change from baseline of 7 or more (decrease or increase) and of 10 or more (decrease or increase) will be provided for each post-baseline assessment.

Missing data

1. If – for a questionnaire – one (or more) dimensions of the descriptive system are missing then
 - The EQ-5D VAS will be included in the analysis
 - The valuation index will not be included in the analysis
 - The non-missing dimensions of EQ-5D descriptive system will be included in the analysis of the separate dimensions
2. If – for a questionnaire – the EQ-5D VAS is missing then
 - the EQ-5D descriptive system and valuation index will be included in the analysis if complete (otherwise see 1)

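### Attachment 5 of the SAP, the scoring table for the EQ-5D index, omits 25 of the 3,125 health states and prints one state twice

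*SAP*

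**What the plan says.** SAP 5.3.1.2 states that the EQ-5D "descriptive system consists of 5 dimensions", "with 5 possible levels", and that "A health state is a combination of 5 level codes; one level code for each dimension". The digits follow the order mobility, self-care, usual activities, pain/discomfort, anxiety/depression. The scoring step is to "Assign an index value to each health state as defined in Attachment 5". The same item mentions a weighting formula and its source ("The algorithm is based on the valuation of EQ-5D health states using the UK TTO"), but no weights are printed anywhere in the SAP.

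The index is listed as a baseline characteristic in SAP 4.1. SAP 5.3.2.2 summarises it as actual value and change from baseline, descriptively and with mean (SE) plots per visit. The only missing-data rule for the index is also in 5.3.2.2: when one or more dimensions are unanswered, "The valuation index will not be included in the analysis". Nothing is said about a fully answered questionnaire whose state is absent from the table.

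**The concern.** Attachment 5 is an operational look-up. As the SAP is written, it is the only scoring rule that a programmer can apply from the document alone. A gap in it turns a valid, complete response into a missing index value without any rule that says so.

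The gap is not spread evenly over the scale. Self-care level 5 is worded "I am unable to wash or dress myself", and every missing state carries it, so any loss would fall on subjects in poor states. The Time and Events Schedule collects the EQ-5D at baseline and on Days 6, 14 and 28. Change is defined as the post-baseline value minus the baseline value, so one unscored baseline state can cost three change values as well as the baseline value itself.

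**Working it through.** **How many states there should be.** Five dimensions with five levels each give 5^5 = 3,125 states.

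**Where the table breaks.** Two consecutive printed rows of Attachment 5 read:

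| Column 1 | Column 2 | Column 3 | Column 4 |
|---|---|---|---|
| 15254 | 15443 (0.082) | 21232 | 21421 |
| 15255 | 15544 (-0.038) | 21233 | 21422 |

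Columns 1, 3 and 4 advance by one state. Column 2 jumps. The skipped states are:

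- 15444-15445: 2
- 15451-15455: 5
- 15511-15515: 5
- 15521-15525: 5
- 15531-15535: 5
- 15541-15543: 3

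Total: 2 + 5 + 5 + 5 + 5 + 3 = 25.

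**Is it text lost in reading the PDF?** No. The affected column prints 44 entries, the same as its three neighbours, and every row across the gap has all four state/value pairs. From its first to its last entry (15331 to 21114) the column should hold 69 consecutive states, and 69 - 44 = 25. The next column continues correctly at 21115.

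**Is it the only gap?** The table has 18 pages. Page 1 has 4 columns of 41 entries, pages 2 to 17 have 4 columns of 44, and page 18 has columns of 44, 44 and 33:

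4 × 41 + 16 × 4 × 44 + (44 + 44 + 33) = 164 + 2,816 + 121 = 3,101 entries.

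State 24155 ends one column and starts the next, at -0.16 both times, so there are 3,101 - 1 = 3,100 distinct states. 3,125 - 3,100 = 25. The tally closes, so there is no second gap.

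**Could 15544 be a misprint for 15444?** No. At self-care level 5 the table has a constant step between mobility 1 and mobility 2:

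- 15443 and 25443: 0.082 - 0.025 = 0.057
- 15544 and 25544: -0.038 - (-0.095) = 0.057
- 15555 and 25555: -0.280 - (-0.337) = 0.057

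State 15444 should then be 25444 + 0.057 = -0.056 + 0.057 = 0.001. The printed -0.038 fits 15544, so the label is right and the rows before it are absent.

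**What values are missing.** Applying the same step to the printed mobility-2 states:

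- highest: 15511 = 0.285 + 0.057 = 0.342
- lowest: 15455 = -0.298 + 0.057 = -0.241

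The range is 0.342 - (-0.241) = 0.583. These values are inferred, not printed.

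**Possible effect on a mean.** If one subject with value m drops out of n, and the remaining subjects have mean R, the reported mean shifts by (R - m)/n. It rises whenever R exceeds m. For an upper bound, take n = 300 per arm (the 600 infected subjects of the sample-size section, split 1:1, all assessed), R = 1 (the maximum index) and m = -0.241. The shift is at most 1.241/300 = 0.004 per lost subject.

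For change from baseline the sign depends on where the loss occurs. Losing a subject who started in a missing state removes someone with much room to improve, which can understate mean improvement. Losing a post-baseline value in a missing state removes a poor result, which can overstate it.

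**The case against.** The strongest reply is that SAP 5.3.1.2 does not rest on the printed table alone. It describes a formula and names a UK time trade-off value set, and a programmer who works from that source scores all 3,125 states. This stands. A reader might infer that subjects in these states will certainly go unscored, and the documents do not support that: the loss arises only if Attachment 5 as printed is the look-up. The reply does not remove the defect, because the weights are not in the SAP and going to the source would depart from the instruction to use Attachment 5.

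Exposure is probably very small. The missing states require no difficulty walking together with complete inability in self-care and severe or extreme problems with usual activities. Subjects must also not need hospital care at screening (protocol 4.1, criterion 4). This stands too, although the documents give no frequencies of EQ-5D states.

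The index has no inferential role. It is not tested, it is outside the hierarchy in SAP 5.1.1, and the five dimensions and the VAS are summarised separately and are unaffected. The duplicate 24155 has the same value twice and changes no score, although a merge on a repeated key can duplicate a record.

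Two further readings should be resisted. The gap is 25/3,125 = 0.8% of states, which is not 0.8% of subjects. The values bordering the gap (0.082 and -0.038) do not describe its contents, which span about 0.58.

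**Conclusion.** The omission is real and can be checked on the page: 25 states are missing and one is duplicated. Used as printed, the table leaves a complete response in any of these states without an index and, if this happens at baseline, without any change from baseline.

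The practical size is minor. The bound on a mean is about 0.004 per lost subject in an arm of 300, and few such subjects are likely. The upward direction applies to the mean level and assumes that the remaining subjects average higher than those lost. It should not be carried over to mean change. The inferred range of about 0.34 to -0.24 assumes that the 0.057 mobility step holds throughout self-care level 5, as it does in the pairs checked. A reader might go on to infer that the trial's efficacy conclusions are at risk. They are not, because no primary or confirmatory result uses the index.

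**What to change.** Add the 25 missing rows to Attachment 5 from the same UK TTO-based value set. Take the values from the source, and use the inferred ones only as a cross-check. Delete the second 24155 row. Add a programming check that the look-up holds 3,125 unique states with one value each, and that every complete questionnaire returns exactly one index value. The cost is one table correction and one check, with no effect on any other analysis.

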5.3.1.3. Clinical outcomes

Measurement	Formula
Incidence of treatment-emergent adjudicated influenza complications	
The incidence of treatment-emergent adjudicated influenza complications from first intake of study drug until the end of the study will be categorized in a hierarchical fashion.
 
The overall category will consist of any complication.
 
The following subcategories are defined:
 
 ▪ Pulmonary complications: 
 • respiratory failure, • primary viral pneumonia, • secondary bacterial pneumonia, • exacerbations of chronic underlying pulmonary diseases, • bronchitis • other complications ▪ Extrapulmonary complications: 
 • Cardiovascular and cerebrovascular disease (eg, myocardial infarction, congestive heart failure, arrhythmia, stroke), • Muscular disorders (eg, myositis, rhabdomyolysis), • Central nervous system (CNS) involvement, • Acute exacerbation of chronic kidney disease, • Severe dehydration, • Decompensation of previously controlled diabetes mellitus, • Other infections (eg, sinusitis, otitis) • Other complications ▪ Pulmonary complications including sinusitis and otitis ▪ Major / minor complications ▪ Infectious / non-infectious complications 
The complications sinusitis and otitis are determined based on their MedDRA preferred terms as listed in Attachment 1, Table 6, for the protocol terms ‘Sinus infection’ and ‘Ear infection’ respectively. Only those terms that are judged to be complications by the adjudication committee will considered for the endpoint ‘pulmonary complications including sinusitis and otitis’.

Incidence of hospital admission 28 days after treatment initiation.	
Was the subject admitted to the hospital? The following medical encounters are considered as indicating hospitalization: ‘Emergency Room’, ‘Intensive Care Unit’, ‘Hospice/Palliative Care Unit’, and ‘Hospital Inpatient Department’. Subjects hospitalized for a preplanned surgery or procedure will not be counted as a hospitalized

	
subject for this endpoint. If a subject is discharged from hospital and subsequently readmitted, the subject will only be counted once as being admitted.
 
Categories will be Yes (1) or No (0).


Incidence of treatment-emergent adjudicated influenza complications including hospitalization
	
The incidence of treatment-emergent adjudicated influenza complications from first intake of study drug until the end of the study or hospitalization 28 days after treatment initiation as defined above.
 
Categories will be Yes (1) or No (0).

Time to resolution of fever (hours) [Time-to event]
	
It is assumed that all subjects will have fever at baseline.
 
The time to resolution of fever is defined as the time in hours from initiation of study treatment to the first of a successive series of 3 recordings for which the fever is resolved (see Table 8). The 3 successive recording may have been done over 4 scheduled successive analysis timepoints, in case of 1 missing in between timepoint.
 
In case the resolution of fever is not achieved, data will be censored.
 
Censoring will be done as follows:
 
 1) Last non-missing record(s) indicate resolution of fever (but insufficient recordings to meet the time to resolution) 
Censoring will be done at the first record of resolution of fever from the last series of recordings of resolution of fever
 2) Last non-missing record does not indicate resolution of fever 
Censoring will be done after the last observation, which is 08:00 on the same day if the last observation was a diary entry from 00:01 until 02:00, 20:00 on the same day if the last observation was a diary entry from 02:01 until 14:00, and 08:00 the next day if the last entry was a diary entry from 14:01 until 00:00.
 
Additionally, in the following cases the subject will be censored using a time-to equal to the maximum time across all subjects:
 
 ○ death, ○ if a subject had not resolved the fever at time of hospitalization and/or during hospitalization and no further data on fever resolution is available

Table 8: Resolution criterion for fever

Assessment	Resolution Criterion
Temperature	temperature as recorded on the ePRO device <37.0°C without the use of antipyretics on that day

The following ATC level 4 codes and generic medication names indicate an antipyretic medication:

- N02BA
- N02BE
- Ibuprofen
- Paracetamol
- Acetylsalicylic acid

If an antipyretic medication misses components of its start and/or stop dates (day and/or month and/or year) the following actions will be taken:

1. In case of partial start date

- If the day is missing, then the day will be the first day of the month (or the day of first dose whichever is later)
- If the month is missing the month will be January (or the months of first dose whichever is later)
- If the year is missing, then the year will be the year of first dose

2. In case of partial end date

- If the day is missing, then the day will be the last day of the month (or the day of last contact with the subject whichever is earlier)
- If the month is missing, then the month will be December (or the month of last contact with the subject whichever is earlier)
- If the year is missing, then the year will be the year from the date of last contact with the subject.

3. In case of a completely missing start date, the antipyretic will be considered as having started before the trial

4. In case of a completely missing end date, the antipyretic medication will be considered as ongoing at the end of the trial.

Antipyretic medication use associated with both the morning and evening temperature recordings for a particular day is also obtained

	from the subject's diary. If a subject indicates that they used an antipyretic 'today' then the date of this assessment indicates antipyretic use on that whole day. If a subject indicates that they used an antipyretic 'yesterday' then this indicates antipyretic medication use on the whole day before the assessment day.
Incidence of all-cause mortality	Did the subject die after first dose of study drug? Categories will be Yes (1) or No (0).

